### **9.2 Correlative studies sample**

Samples should be identified with the patient UPN, the source (e.g. BM: bone marrow, PB: peripheral blood, S: skin; U: buccal), the cycle (e.g. D0: day 0; C1D10: cycle 1 day 10; C1D28; cycle 1 day 28, etc), the month/day/year of collection. Individual tubes or vials may be labeled with a specimen number. Specimen records should be included with each collection.

Peripheral blood and bone marrow samples collected by collaborating institutions should be frozen as viable cells at  $5-10^6$  cells per ml. For convenience, samples can be stored locally in liquid nitrogen and may be shipped in batches to Washington University for further processing, at the address below:

Washington University  
Division of Oncology  
SWT621  
[name]  
[name]

Samples to be collected:

#### Bone Marrow

- Baseline
- C1D10 ( $\pm 2$ )\*\*
- C1D28 ( $\pm 4$ )
- C2D28 ( $\pm 4$ )\*\*\*
- C3D28 ( $\pm 4$ )
- Progression or relapse

After the necessary samples are obtained for optimal medical care of the patient (if applicable), additional aspiration will be performed to obtain a sample for research purposes. The anticoagulated specimen (10 mL) will be placed in sterile EDTA vacutainer tubes, and then the cellular elements of the collected marrow will be separated and

cryopreserved. If at any bone marrow collection the aspirate is a “dry tap”, two additional tubes of blood (10 mL each) will be collected and banked.

\*\* Bone marrow aspirate and biopsies will only be performed in patients enrolled at Washington University.

\*\*\* At the discretion of the treating physician

#### Peripheral Blood

- Baseline
- C1D10 ( $\pm 2$ )
- C1D28 ( $\pm 4$ )
- C2D28 ( $\pm 4$ )
- C3D28 ( $\pm 4$ )
- Progression or relapse

Peripheral blood will be obtained by venipuncture or cannulation of an indwelling venous access device. Ten mL will be placed in sterile EDTA anticoagulated vacutainer tubes which will be processed to cryopreserved cells w/RBC Lyse (up to 15 aliquots at  $1 \times 10^7$  cells/aliquot).

#### Skin Biopsy

- If WBC at time of enrollment is  $< 30,000/\mu\text{l}$ , skin biopsy should be collected during enrollment bone marrow biopsy.
- If WBC at time of enrollment is  $>30,000/\mu\text{l}$ , skin biopsy should be collected at the time of C1D28 bone marrow biopsy or thereafter.

A single 6 mm punch biopsy of normal skin will be performed using standard techniques and local anesthesia. The skin samples will be placed in a sterile specimen cup and snap frozen following collection.

#### Buccal Swab

- Baseline (if skin biopsy is declined)
- C2D28 ( $\pm 4$ )
- Buccal cells should be spun down and snap frozen as a single pellet at the time of collection.

## 10.0 STUDY CALENDAR

	Screening	B/I	C1D1	C1D0	C1D28	C2D1	C2D28	C3D1	C3D28	All cycles thereafter		Time of progression	F/U
										D1	D28		
Informed consent	X												
Medical history	X		X			X		X		X			
Physical exam, ht, wt	X	X 	X			X		X		X		X	
CBC + diff	X	X 	X	-----	X 	X 	X	X 	X	X 		X	
Serum chemistry 	X	X 	X			X		X		X		X	
Pregnancy test 	X	X 											
HIV, hepatitis tests	X 												
BM bx + aspirate 				X 	X 		X 		X 		X 	X	
Flow cytometry 													
PB for research				X 	X 		X 		X 			X	
Skin biopsy													
Buccal swab							X						
Decitabine			X	----	X 		X 		X 		X 		
AE assessment													
Progression/survival													X 

1. Women of childbearing potential only
2. On bone marrow or peripheral blood
3. For BMBX, no more than 28 days prior to the 1st dose of decitabine. For the skin biopsy, if WBC at enrollment is > 30,000/ $\mu$ l, the skin biopsy should be collected during C1D28, or thereafter.
4. No more than 7 days prior to the 1st dose of decitabine
5. Including albumin, creatinine, total bilirubin, AST, ALT, LDH
6. Days 1-10
7. May be reduced to Days 1-5 for Cycles 3 and 4
8. Buccal swab may be performed at baseline in patients who decline skin biopsy
9. Drawn weekly during Cycle 1; may be reduced to Days 1 and 15 of each cycle after Cycle 1
10. Patients who relapse or who have progressive disease (PD) after 2 cycles of decitabine may proceed to alternative salvage regimen or to stem cell transplant per treating physician and center preference.
11. Transplant eligible patients who achieve CR, CRc, CRi, or mLFS after 3 cycles with a suitable donor will proceed to conditioning regimen and transplant; transplant eligible patients who are in PR after 3 cycles will be removed from protocol and proceed to salvage treatment according to center preference; transplant ineligible patients with all responses (CR, CRc or CRi, PR, SD) will continue on maintenance doses until progression or death
12. At the discretion of the treating physician
13. +/- 2 days, only patients enrolled at Washington University
14. Typically 28 +/- 4 days. At the discretion of the treating physician this biopsy may be delayed until the next cycle is initiated. The biopsy at the end of cycle 2 will be collected at the discretion of the treating physician.
15. For 2 years
16. Prior negative screening at any time is sufficient. If no prior screening is available, the patient should be tested during screening.
17. If at any bone marrow collection the aspirate is a "dry tap", two additional tubes of blood (10 mL each) will be collected and banked.

## 11.0 DATA SUBMISSION SCHEDULE

Case report forms with appropriate source documentation will be completed according to the schedule listed in this section.

Case Report Form	Submission Schedule
Original Consent Form	Prior to registration
Patient Registration Form Medical and Surgical History Form Treatment History Form On Study Form Correlative Skin Biopsy Form	Prior to starting treatment
Decitabine Form	End of each cycle
CBC Form	Baseline Day 1 Day 10 Day 28 Time of progression
Correlative Bone Marrow Form Correlative Blood Form	Baseline C1D10 End of Cycle 1 End of Cycle 2 End of Cycle 3 Time of progression or relapse
Correlative Buccal Swab Form	Baseline End of Cycle 2
Disease Assessment Form	Baseline End of Cycle 1 End of Cycle 2 End of Cycle 3 Time of progression
Off Treatment Form	Due at the completion of the EOT visit, at the time of death, and/or at the time that the patient is lost to follow-up
Follow Up Form	30 days post date of last decitabine dose. Every 6 months for 2 years after the last dose of study drug.
Hospitalization Form	Time of hospitalization
Death Form	Time of death
Record of Adverse Events	At the time of any AE

Any queries generated by Washington University must be responded to within 28 days of receipt by the participating site. The Washington University research team will conduct a regular review of data status at all secondary sites, with appropriate corrective action to be requested as needed.

## 11.1 Adverse Event Collection in the Case Report Form

All adverse events that occur beginning with start of treatment (minus exceptions defined in Section 7.0) must be captured in the Toxicity Form. Baseline AEs should be captured on the Medical History Form.

Participant death due to disease progression should be reported on the Toxicity Form as grade 5 disease progression. If death is due to an AE (e.g. cardiac disorders: cardiac arrest), report as a grade 5 event under that AE. Participant death must also be recorded on the Death Form.

## 12.0 MEASUREMENT OF EFFECT

### 12.1 Response assessment

Bone marrow biopsy will be obtained on Cycle 1 Day 28 ± 4, Cycle 2 Day 28 ± 4, and Cycle 3 Day 28 ± 4. The cycle 2 Day 28 collection may be performed at the discretion of the treating physician.

All patients will be assessed for response according to the 2017 ELN AML Recommendations:

*Complete remission (CR)* – Defined as bone marrow blasts <5%; absence of circulating blasts and blasts with Auer rods; absence of extramedullary disease; absolute neutrophil count  $\geq 1.0 \times 10^9/L$  (1,000/ $\mu$ L); platelet count  $\geq 100 \times 10^9/L$  (100,000/ $\mu$ L).

*Complete remission with incomplete hematologic recovery (CRi)*: All CR criteria except for residual neutropenia -  $< 1.0 \times 10^9/L$  (1,000/ $\mu$ L) or thrombocytopenia -  $< 100 \times 10^9/L$  (100,000/ $\mu$ L)

*Cytogenetic complete remission (CRc)* – Defined as morphologic complete remission plus a reversion to a normal karyotype. For this study, reversion of a normal karyotype is defined as no clonal abnormalities detected in a minimum of 20 mitotic cells.

*Morphologic leukemia free state (mLFS)*: Defined as bone marrow blasts <5%; absence of blasts with Auer rods; absence of extramedullary disease; no hematologic recovery required. Marrow should not merely be “aplastic”; at least 200 cells should be enumerated or cellularity should be at least 10%

*Partial remission (PR)* – Defined as all hematologic criteria of CR; decrease of bone marrow blast percentage to 5% to 25%; and decrease of pretreatment bone marrow blast percentage by at least 50%.

*Stable Disease (SD)* – Defined as not meeting the definitions of CR, CRi, PR, PD, or recurrence/morphologic relapse.

*Progressive disease (PD)* – Defined as a clear increase in bone marrow blast count, typically a greater than 50% increase compared with baseline, or new extramedullary disease. Patients with a > 50% increase in peripheral blast count with an increase of the total peripheral white blood cell count to > 10,000/ $\mu$ l should undergo evaluation by bone marrow biopsy to assess for progressive disease. Patients enrolled with a bone marrow blast count < 20% will have > 20% blasts and a > 50% increase compared with baseline.

*Recurrence/morphologic relapse* - Defined as relapse following complete remission is defined as reappearance of blasts in the blood or the finding of  $\geq$  5% blasts in the bone marrow, not attributable to any other cause. New dysplastic changes is considered relapse. If there are no blasts in the peripheral blood and 5-20% blasts in the bone marrow, bone marrow biopsy should be repeated in > 1 week to confirm relapse.

#### **A. Duration of Response and Stable Disease, Treatment Failure, Overall Survival and Event-free Survival**

**Duration of overall response:** The duration of overall response is measured from the time measurement criteria are met for CR or PR (whichever is first recorded) until the first date that recurrent or progressive disease is objectively documented

The duration of overall CR is measured from the time measurement criteria are first met for CR until the first date that progressive disease is objectively documented.

**Duration of stable disease:** Stable disease is measured from the start of the treatment until the criteria for progression are met, taking as reference the smallest measurements recorded since the treatment started, including the baseline measurements.

Treatment failure is defined as death or failure to achieve a complete or partial remission following 4 cycles of therapy.

Overall survival is defined as the date of first dose of study drug to the date of death from any cause. Patients still alive at the time of the final analysis will be right-censored.

Event-free survival is defined as the interval from the date of first dose of study drug to date of treatment failure, recurrence, death due to any cause, or loss to follow up.

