#### **B. Duration of Remission and Relapse-free Survival for Patients Having Complete Remission**

Duration of complete remission is defined as the interval from the date that complete remission is documented to the date of recurrence, death due to any cause, or loss to follow-up.

Relapse-free survival is defined only for those patients achieving a CR or CRi. It is defined as the interval from the date of first documentation of a leukemia-free state to the date of recurrence, death due to any cause, or loss to follow up.

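### Section 12.1.A ends the duration of overall CR only at progressive disease, so some relapses end the overall response but not the CR, and Section 12.1.B gives a different CR duration from the same data

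*Combined protocol and SAP*

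**What the plan says.** Section 12.1.A gives two duration rules one after the other. Overall response runs from when criteria are "met for CR or PR (whichever is first recorded) until the first date that recurrent or progressive disease is objectively documented". Overall CR runs from when "measurement criteria are first met for CR until the first date that progressive disease is objectively documented". The second rule does not mention recurrence.

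Section 12.1.B then defines a duration of complete remission as the "interval from the date that complete remission is documented to the date of recurrence, death due to any cause, or loss to follow-up".

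The two end events are defined separately in Section 12.1. Progressive disease is a clear rise in marrow blasts, "typically a greater than 50% increase compared with baseline, or new extramedullary disease". A floor is added for low baselines: "Patients enrolled with a bone marrow blast count < 20% will have > 20% blasts and a > 50% increase compared with baseline". Recurrence after CR is the "reappearance of blasts in the blood or the finding of" at least 5% marrow blasts; new dysplastic changes also count.

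Section 5.1 describes progression and relapse together, for removal from protocol, as more than 20% marrow blasts with a rise of at least 50% from the prior biopsy. Its reference is not baseline.

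The first secondary objective in Section 2.2 counts both CR and CRi as responses.

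**The concern.** Once a patient is in CR, the event that ends the remission is recurrence. A rule that stops only at progression, typically judged against pre-treatment blasts, lets a patient relapse without ending the CR. Two problems follow. A CR can outlast the overall response that contains it, which is incoherent. And 12.1.A and 12.1.B give two CR durations for the same patient, with nothing to say which is to be reported.

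The start of overall response has a related gap. CRi is left out, although the protocol treats CRi as a response.

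At stake is whether any reported remission or response duration has a single, reproducible meaning.

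**Working it through.** The documents give no event count, power or expected value for these durations, so there is no stated figure to reproduce. The check compares the rules and then their thresholds.

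**1. The three rules side by side**

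| Duration | Starts | Ends |
|---|---|---|
| Overall response (12.1.A) | first of CR or PR | recurrence or progression |
| Overall CR (12.1.A) | CR | progression only |
| Complete remission (12.1.B) | CR | recurrence, death or loss to follow-up |

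Progression is one of the two events that end overall response. So the overall CR can never end earlier than the overall response, and it ends later whenever a recurrence is not also progression.

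**2. The marrow thresholds (Section 12.1)**

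Let b be baseline marrow blasts in percent.

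- Recurrence: at least 5%, whatever b is.
- Progression, typical rule: above max(20, 1.5 × b) if b is below 20; above 1.5 × b otherwise.

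| Baseline b | Progression needs more than | Marrow relapses that are not progression |
|---|---|---|
| 10% | max(20, 15) = 20% | 5-20% |
| 15% | max(20, 22.5) = 22.5% | 5-22.5% |
| 20% | 30% | 5-30% |
| 30% | 45% | 5-45% |
| 40% | 60% | 5-60% |
| 50% | 75% | 5-75% |
| 60% | 90% | 5-90% |
| 66.7% or more | 100% or more | all, by the marrow rule alone |

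The 5-20% band is common to every row. It also remains under the prior-biopsy wording of Section 5.1: marrow blasts in CR are below 5%, so a 50% rise needs at most 1.5 × 5 = 7.5%, and the binding condition is more than 20%.

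**3. A worked case (hypothetical)**

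Baseline blasts 40%, then CR, then relapse at month 7 with 30% marrow blasts and no new extramedullary disease.

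- Overall response ends at month 7, by recurrence.
- Complete remission (12.1.B) ends at month 7.
- Overall CR (12.1.A) continues, because 30% is below 1.5 × 40% = 60%. Under the Section 5.1 reference it would end, because 30% exceeds 20% and is more than 50% above a prior biopsy below 5%.

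A patient who dies in CR ends complete remission under 12.1.B but never ends overall CR under 12.1.A.

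**4. How many relapses are affected**

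The documents give no distribution of blasts at baseline or relapse. Under assumed uniform distributions, the percentage of marrow relapses short of progression by the typical rule is:

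| Baseline blasts | Relapse 5-20% | Relapse 5-50% | Relapse 5-100% | Relapse 20-100% |
|---|---|---|---|---|
| 0-20% | 100 | 37 | 18 | 2 |
| 5-30% | 100 | 52 | 25 | 10 |
| 5-100% | 100 | 87 | 69 | 63 |
| 20-80% | 100 | 95 | 71 | 66 |

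The range is about 2% to 100%, which only shows that the share depends on the assumptions.

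**5. The start of overall response**

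By Section 12.1, CRi has marrow blasts below 5% without full count recovery. It is not CR, because the counts fall short. It is not PR, because PR needs 5-25% blasts and the count criteria of CR. A patient whose best response is CRi, with no earlier PR, has no start date. One who later reaches CR starts late.

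**The case against.** The strongest reply is that little depends on this rule. Neither 12.1.A duration is a listed endpoint in Section 2, and Section 15 plans no analysis of either. Section 12.1.B already ends remission at recurrence, and its relapse-free survival includes CRi. That stands, and it limits the impact.

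The progression cut-off is also softer than a fixed 1.5 × baseline. Section 12.1 says typically, new extramedullary disease is progression at any blast count, and Section 5.1 refers to the prior biopsy. This stands too: the upper rows of the threshold table are one reading. It does not rescue the 5-20% band. That band fails the 20% condition in Section 5.1 and the floor for patients enrolled below 20%, and for higher baselines it is no increase over baseline. The smallest-measurement reference in 12.1.A is attached to stable disease, not to CR.

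Two stronger readings are tempting. A reader might infer that most relapses would fail to end the CR. The documents give no blast distributions, so that cannot be shown. A reader might also infer that time to leukemia relapse, compared with 6-8 months in Section 2.2, would be inflated. Nothing ties that endpoint to the 12.1.A rule. Its name points to the recurrence definition, and Section 15.4.E says only that it will be summarized descriptively. Its missing definition is a separate gap in detail.

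**Conclusion.** The inconsistency is real and rests on the text alone. Section 12.1.A ends overall CR at the wrong set of events, contradicts the sentence before it, and conflicts with 12.1.B. At least those relapses with 5-20% marrow blasts and no new extramedullary disease end the response but not the CR. Under the typical baseline rule, more do so as baseline blasts rise. The CRi start-date gap is also real.

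The size cannot be stated as a share of relapses. The consequence is confined to descriptive remission and response durations. The 1-year overall survival endpoint, the 60-patient sample size and the analyses in Section 15 do not rest on this rule. It should be corrected, but it does not threaten the trial's main conclusion.

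**What to change.** 1. Delete the sentence on duration of overall CR in 12.1.A and keep 12.1.B as the single definition, or rewrite it to end at recurrence, progression or death. If 12.1.B is kept alone, add new extramedullary disease as an end event: Section 12.1 names it under progression but not under recurrence.
2. State that loss to follow-up is censoring at last assessment. Section 12.1.B now lists it beside recurrence and death.
3. Start duration of overall response at the first of CR, CRi or PR.
4. Reconcile the reference for progression in Section 5.1 (prior biopsy) with that in Section 12.1 (baseline). Which is appropriate is for the sponsor to decide.

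The cost is wording in Sections 5.1 and 12.1, with no new visits or data items. CR durations will be shorter than under the present 12.1.A rule for patients who relapse short of progression or die in remission, and CRi patients will gain a response start date.

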**SCHEMA**

A bone marrow biopsy may be performed at any time after Cycle 2 if there is clinical concern for progression.

Patients with progressive disease after 2 cycles of decitabine (10 days each) may be removed from study.

After Cycle 2, decitabine dose will be reduced FOR ALL PATIENTS from 20 mg/m^2/day x 10 days to 20 mg/m^2/day x 5 days. After Cycle 1, patients with blast counts <5% may reduce decitabine dose from 20 mg/m^2/day x 10 days to 20 mg/m^2/day x 5 days. Each cycle is 28 days.

Notes for transplant eligible patients

Anytime after 3 cycles, transplant eligible patients in **CR, CRc, CRi, or mLFS\*** should **proceed to stem cell transplant** according to institutional protocols.

After 3 cycles, transplant eligible patients in **PR\*** may be removed from study and proceed to salvage according to institutional protocols.

Notes for transplant ineligible patients

Transplant ineligible patients **will continue on study with decitabine (x 5 days)** until relapse or progression, with the exception of patients with **SD\*** after 4 cycles who may continue on therapy or be removed from study per treating physician preference.

Antimicrobial prophylaxis during therapy is strongly recommended due to anticipated neutropenia. Common agents include acyclovir, ciprofloxacin, and fluconazole. Alternative agents may be used at the discretion of the treating physician.

Correlative samples:

BM and PB should be collected on Cycle 1 Day 0 (C1D0), Cycle 1 Day 10 (C1D10)\*\*, Cycle 1 Day 28 (C1D28), Cycle 2 Day 28 (C2D28)\*\*\* and Cycle 3 Day 28 (C3D28). A skin biopsy should be done on C1D0 (buccal swab may be substituted for skin if patient declines skin biopsy). A buccal swab should be done on C2D28. BM and PB should be collected at the time of progression (if possible).

\*For definition of responses see Section 12

\*\* Bone marrow aspirate and biopsies on cycle 1 day 10 will only be performed in patients enrolled at Washington University.

\*\*\* At the discretion of the treating physician.

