### **5.0 INVESTIGATION PLAN**

#### **5.1 Summary**

See Section 10 for synoptic table.

Patients will receive decitabine 20 mg/m^2/day as a 1-hour infusion on consecutive days 1-10 of each 28-day cycle. Decitabine dose will be calculated on baseline weight (obtained within a week of the start of cycle 1). Decitabine dose should be recalculated for weight changes above or below 10% from baseline weight

Patients with clinical evidence of progressive disease or relapse (see Section 12 for definitions) should undergo a bone marrow biopsy to evaluate for progression.

After 2 cycles, patients with progressive disease or relapse (a clear progression with at least >20% bone marrow blasts and an increase of at least 50% from prior biopsy) should be removed from protocol and proceed to salvage treatment according to center preference.

Transplant eligible patients with PR after 3 cycles, may be removed from protocol and proceed to salvage treatment or transplant according to center preference.

Transplant eligible patients with a suitable donor who achieve mLFS, CR, CRc, or CRi, may proceed to transplant after at 3 cycles (Section 5.5).

Transplant ineligible patients with CR, CRc or CRi, PR will continue on maintenance doses (see below and Section 6.3) until progression or death, whichever occur first.

Transplant ineligible patient with SD after cycle 4 may be removed from protocol and proceed to alternative treatment or continue on protocol according to treating physician's preference.

After Cycle 1, patients with blast counts < 5% may reduce decitabine dose from 20 mg/m^2/day x 10 days to 20 mg/m^2/day x 5 days.

For all other patients, after Cycle 2, decitabine administration dose will be decreased to 20 mg/m^2/day for 5 consecutive days (Days 1-5) every 28 days (unless otherwise specified) to limit myelosuppressive toxicity.

Peripheral blood sampling and bone marrow biopsies with aspirate will be performed pre-study, on Cycle 1 Day 10 ± 2, Cycle 1 Day 28 ± 4, on Cycle 2 Day 28 ± 4, on Cycle 3 Day 28 ± 4, and at progression or relapse. Patients will provide a skin biopsy sample pre-study; a buccal swab can be performed for patients who decline skin biopsy. A buccal swab will be collected on Cycle 2 Day 28 ± 4.

Following Cycle 3, bone marrow biopsies should be performed at the discretion of the treating physician to assess for response and for relapse or progression.

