### **5.4 Relapsed or Progressive Disease**

Patients who relapse or who have progressive disease (PD) after 2 cycles of decitabine, may proceed to alternative salvage regimen or to stem cell transplant according to treating physician and to center preference. (Please refer to Section 12 for the definition of PD.)

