## **6.0 DOSE DELAYS/DOSE MODIFICATIONS**

A criterion for discontinuation of the study is a delay of > 12 weeks between any two cycles. Dose delays and modifications are allowed as specified below.

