## **E. Secondary Clinical Endpoints Analyses**

The principal measurement of toxicity will be a measure of the total number hospitalized days during the first 60 days of therapy.

**CRc rate** will be analyzed based on the ITT population. The remission rate and its 2-sided 90% confidence interval (CI) will be summarized.

**Event-free survival:** EFS will be analyzed using Kaplan-Meier methodology and Kaplan-Meier plots will be provided using the ITT analysis set. The median EFS and its 2-sided 90% CI using the complementary log-log transformation method (Collett 1994) will be calculated.

**Leukemia-free survival:** LFS will be analyzed using Kaplan-Meier methodology

and Kaplan-Meier plots will be provided using the ITT analysis set. The median LFS and its 2-sided 90% CI using the complementary log-log transformation method (Collett 1994) will be calculated.

**Time to leukemia relapse:** TTCR will be summarized using descriptive statistics.

The time to stem cell transplant, the proportion of patients who are able to undergo transplantation, and the average number of hospital days during cycles 1 and 2, will also be documented. The association between response and clinical characteristics (morphologically evident disease -i.e., >5% blasts by cytomorphology- versus molecularly detected disease at the time of enrollment -i.e., disease detected with flow cytometry, cytogenetic, or mutational analysis with  $\leq 5\%$  blasts by cytomorphology-, *de novo AML versus secondary AML versus treatment-related AML*, presence *versus* absence of cytogenetic abnormalities in addition to *TP53* mutations, etc.) will be described using contingency tables and compared by Chi-square test or Fisher's exact test as appropriate. The association between survival (OS, EFS, LFS) and clinical characteristics will be described using Kaplan-Meier methods and compared by log-rank test.

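### A never-responder who stops decitabine before completing Cycle 4 has no EFS event until death or loss to follow-up, so early exit can lengthen EFS

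*Combined protocol and SAP*

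**What the plan says.** Section 12.1.A measures EFS from first dose "to date of treatment failure, recurrence, death due to any cause, or loss to follow up". It then defines the first of these events: "Treatment failure is defined as death or failure to achieve a complete or partial remission following 4 cycles of therapy". Section 12.1 limits recurrence to patients who have been in remission ("Defined as relapse following complete remission"). It also defines progressive disease, but 12.1.A does not list progression as an EFS event.

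Decitabine can end before Cycle 4 in a patient who has not responded:

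- **Progression or relapse after 2 cycles.** Section 5.1 says such patients "should be removed from protocol and proceed to salvage treatment according to center preference". The Schema is permissive: "Patients with progressive disease after 2 cycles of decitabine (10 days each) may be removed from study". So is 5.4: "Patients who relapse or who have progressive disease (PD) after 2 cycles of decitabine, may proceed to alternative salvage regimen".
- **Hydroxyurea still needed after Cycle 2.** Section 5.7.A takes this as evidence of non-response and says decitabine should stop.
- **Delay.** Section 6.0: "A criterion for discontinuation of the study is a delay of > 12 weeks between any two cycles".
- **Other exits.** Section 5.8 lists adverse events, decline in condition, withdrawal and investigator decision.

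The EFS analysis is in 15.4.E: "EFS will be analyzed using Kaplan-Meier methodology and Kaplan-Meier plots will be provided using the ITT analysis set". That set is every patient with at least one dose (15.2). The plan reports a median with a 90% CI and compares EFS between clinical subgroups by log-rank test.

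**The concern.** The non-response part of the endpoint has a date only for patients who complete 4 cycles. A refractory patient who leaves sooner stays in the analysis set, and Section 5.1.J continues to record subsequent therapy, progression and death. Until death or loss to follow-up, however, nothing that happens to that patient counts as an event. A refractory patient who stays on treatment fails at the end of Cycle 4.

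The failure rule also does not require the remission to have come from decitabine. A remission reached on later salvage is therefore not excluded and could be argued to avert failure.

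The EFS curve would then depend partly on how often centers take refractory patients off treatment early, and more early exits would make it look better. If subgroups differ in that practice, the log-rank comparisons would partly measure exit practice.

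**Working it through.** The documents give no EFS figure to reproduce. The check traces the rule and then illustrates its size.

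**1. Which event can a never-responder who stops at day 56 have?**

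- Failure by non-response: needs 4 cycles, not reached.
- Recurrence: needs a prior complete remission, not available.
- Progression: not an EFS event.
- Death or loss to follow-up: available.

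No other section supplies a failure date.

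**2. Inputs.** From the documents:

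- 28-day cycles (Schema), so 2 cycles end at day 56 and 4 cycles at day 112.
- 1-year OS of 25% (historical) and 40% (target) in 15.4.G.
- Median survival of only a few months with standard therapy in the adverse-karyotype population, often *TP53*-mutated (1.1).

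Assumed:

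- Exponential survival, and 30% responders.
- Relapse in responders from day 84, exponential with a 7-month median (the middle of the 6-8 months in 2.2).
- A fraction f = 25%, 50% or 75% of non-responders leaving at day 56.

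**3. One patient.** A leaver alive at day 56 outlasts a day-112 failure with probability exp(−h × 56), where h is the daily death hazard.

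| Survival assumed after exit | P(alive past day 112) |
|---|---|
| 1-year OS 40%: h = 0.916/365.25 | 87% |
| 1-year OS 25%: h = 1.386/365.25 | 81% |
| median 4 months | 73% |
| median 3 months | 65% |
| median 2 months | 53% |

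Longer EFS for the leaver is more likely than not across this range, but not certain.

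**4. Six-month EFS, 1-year OS 40%.** Survival to 6 months is 0.40^0.5 = 0.632.

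- Responders: 0.632 × exp(−0.693 × 98.6/213.1) = 0.459. Their contribution is 0.30 × 0.459 = 0.138.
- Non-responders who stay contribute 0, having failed at day 112.
- Leavers scored as failures, at day 56 or day 112, also contribute 0. The total is **14%**.
- Leavers scored at death contribute 0.70 × f × 0.632 = 0.443f. The total is 0.138 + 0.111, 0.221 or 0.332, that is **25%, 36% or 47%**.

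If instead non-responders have a 3-month median survival, their 6-month survival is 0.25. Leavers add 0.70 × f × 0.25 = 0.175f, and the total is **18%, 23% or 27%** against 14%.

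For scale, the binomial standard error at n = 60 is √(0.14 × 0.86/60) = 4.5 points at 14% and √(0.47 × 0.53/60) = 6.4 points at 47%.

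**5. Median EFS, the statistic 15.4.E names (1-year OS 40% for all).** Survival to day 112 is 0.755. For responders, event-free survival to day 112 is 0.755 × 0.913 = 0.689. With leavers scored at death, the curve just after day 112 is 0.30 × 0.689 + 0.70 × f × 0.755 = 0.207 + 0.529f, which is 0.34, 0.47 or 0.60. Just before day 112 it is 0.735. The median is therefore day 112 unless f is large.

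| Leaving early | Scored at death | Scored at day 112 | Scored at removal (day 56) |
|---|---|---|---|
| 25% | 112 | 112 | 112 |
| 50% | 112 | 112 | 97 |
| 75% | 165 | 112 | 56 |

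**The case against.** Several points on the other side are sound.

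- **Stronger readings of the text.** A reader might infer that the protocol sends non-responders off after 2 or 3 cycles. It does not. The response-based exits tied to Cycle 3 are transplant in remission or mLFS and removal in PR, and PR is a remission under the failure definition. Stable disease is a response-based exit only after Cycle 4, for transplant-ineligible patients. After 2 cycles the wording is *should* in 5.1 and *may* in the Schema and 5.4; those passages must be reconciled. A reader might also infer that failure is never scored before 4 cycles, but death already counts.
- **Overlap with the missing progression event.** Listing progression would close the main early route. It would not close stops for hydroxyurea need, delay, toxicity or choice without documented progression. The documents do not allow that remainder to be sized.
- **Size.** A reader might infer that the reported median must move a great deal. With common survival and scoring at death it stays at day 112 at 25% and 50% leaving. Giving refractory leavers the trial's target survival is generous, and the 3-month case shrinks the 6-month shift to about 4 to 13 points. The leaving fractions have no source in the documents.
- **Importance.** Overall EFS is not among the objectives in 2.2, which names only EFS after transplant.

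A charitable reading is that failure means never in remission by the time of Cycle 4. Even so, the text gives no failure date for someone who stopped at Cycle 2.

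**Conclusion.** The point stands in a limited form. Following the rule as written leaves early-stopping never-responders without an EFS event until death or loss to follow-up, and they can outlast comparable patients who stay and fail. This is a fault in the rule, because applying it exactly favors early exit.

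Under the stated assumptions, 6-month EFS is raised by 11 to 33 points with common 40% 1-year survival, and by about 4 to 13 points if non-responders have a 3-month median. The median is affected less consistently: it depends on the leaving fraction and on the date used instead. The true size is unknown, because response, early leaving and survival after exit are all assumed.

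The effect is confined to the EFS curve, its median and the EFS subgroup tests in 15.4.E. The documents do not support extending it to the 1-year OS primary endpoint or to the interim futility rule, which both use death alone.

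**What to change.** Amend the treatment-failure definition in 12.1.A as follows:

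1. Before completing Cycle 4, a patient without a qualifying response on decitabine is a treatment failure on the earliest of documented progression, permanent stop of decitabine, or start of other anti-leukemic therapy.
2. Name the qualifying responses, including CRi, CRc and mLFS. Otherwise patients transplanted in those states could be scored as failures when the next therapy starts.
3. Do not count responses first met after other anti-leukemic therapy has started.
4. For patients still on treatment without response, date failure at the end of Cycle 4 using the latest available assessment. Section 11.0 schedules no disease assessment then, and 5.1 leaves marrow after Cycle 3 to the physician's discretion.
5. Conventions differ on stops for toxicity or withdrawal, so report a sensitivity analysis that does not count them as failures.

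The cost is one definition and one extra analysis. Reported EFS becomes less favorable. The sponsor must also confirm that the case report forms capture the stop and next-therapy dates, because 11.0 lists form names and timing but not fields. No treatment rule changes.
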